15.1 Intervention Group

15.1.1 Participants who receive NRT samples and whose quit day is within one week after baseline

A TWGHs nurse who is experienced in delivering smoking cessation will contact the participants around one week after baseline. The nurse will provide more intensive counseling to the smoker, especially on the use of NRT. All the smokers will be asked if

they have used any NRT and have any difficulties in using NRT, and will be given more counseling via telephone if necessary.

15.1.1.1 Participants who have used NRT

The TWGHs nurse will encourage him/her to obtain additional free NRT by enrolling in the SC clinics for the continuation of NRT use. If the smoker is unwilling to enroll, the nurse will advise him/her to purchase NRT over-the-counter. Other SC services will also be introduced or referred if the participant wants more other services.

15.1.1.2 Participants who have not used NRT but is willing to use later

The TWGHs nurse will advise him/her to use as soon as possible and invite him/her to receive one more follow-up within 1 month as long as the smoker provides the contact number and agrees to be contacted.

15.1.1.3 Participants who show no interest to quit

The TWGHs nurse will use the “5R” approach to re-motivate the quitting intention. The “5R” approach is being adopted by the local and international smoking cessation guideline including the discussion on why quitting is important (relevance), hazards of smoking (risk), benefits of quitting (rewards), difficulties (roadblocks) and repeated quit attempts (repetition).

15.1.1.4 Participants who have contra-indication(s) to NRT

If the smoker tells the nurse that he/she has contra-indication(s) to NRT, the nurse will advise him/her to stop using NRT to avoid risks.

15.1.1.5 Participants who continue smoking during the use of NRT

If the smoker has a dual use of cigarettes and NRT, the nurse will advise him/her to stop using NRT to avoid overdose.

15.1.2 Participants who receive NRT samples and whose quit day is more than one week after baseline

The research assistant will contact the participants around one week after baseline. The participants will receive motivational messages to encourage them to quit and enroll in the

SC clinics if they have not. They will also be asked if they need to contact the TWGHs counsellors for early cessation support. Otherwise, the participants will be contacted by the TWGHs nurse around one week after their quit day as outlined above in section 15.1.1.

15.1.3 Participants who do not receive NRT samples but make an intake appointment within one week after baseline

A TWGHs nurse will contact the participants within one week after baseline reminding them to attend the intake session. The nurse may contact some participants via phone for provision of further counselling or encouragement if necessary.

15.1.4 Participants who do not receive NRT samples but make an intake appointment more than one week after baseline

The research assistant will contact the participants around one week after baseline. The participants will receive motivational messages to encourage them to quit. They will also be asked if they need to contact the TWGHs counsellors for early cessation support. The participants will receive reminder message from the TWGHs nurse before their intake appointment.

15.1.5 Participants who do not receive NRT samples and do not make an intake appointment

The participants will receive motivational messages from the research assistant around one week after baseline to encourage them to quit and enroll in one of the SC clinics.

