Smokers are addicted to tobacco because tobacco delivers nicotine to the central nervous system, which leads to the desired psychological reactions and induces dependence. In the early phase of quitting, the lack of nicotine causes withdrawal symptoms such as headache, coughing, difficulty in concentration etc. By slowly delivering nicotine to cope with the dependence, nicotine replacement therapy (NRT) is a safe and effective pharmacotherapy to reduce withdrawal symptoms during early abstinence and smoking reduction, which increases the quit rate by 4-fold in the longer term [16]. A recent study has shown that NRT works better than many other behavioral interventions for smoking cessation [17]. Although NRT can be purchased over the counter without doctor's prescription, or obtained freely from local SC clinics, only 9.8% of quit attempters had used medications for their quit attempts [9]. The corresponding proportion in Australia, Canada, the UK and the USA is at least 30% [18, 19]. In contrast, over 80% of Hong Kong quit attempters relied on self-determination [9], which has a low success rate and easily leads to smoking relapse. The low prevalence of using NRT may be due to the higher absolute price of NRT per day (US\$5.43 per day) [8] than, say, in the USA (US\$2.41–3.62 per day) [20], and the low utilization of SC services which provide free NRT.

Although some social marketing of SC has been done in Hong Kong, very few programmes promote the use of NRT. Existing SC services provide free NRT to smokers, but the smokers must first enroll in the SC services. That means majority of smokers, who do not know or use SC services, have low literacy of NRT use and its effectiveness.

To sum up, the following health care needs regarding SC promotion in Hong Kong should be addressed: (1) Many current smokers still have no quitting intention (2) Many smokers are unable to quit smoking using self-determination, (3) The low success rate of quitting is attributed to the under-utilization of existing SC service and low use of effective medications such as NRT.

Literature review on others' strategies to address these needs

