In the experimental sessions, the SCAs will approach and distribute souvenirs (e.g. a pen) or leaflets to the smokers at outdoor smoking hotspots for 3-4 hours. The souvenirs and leaflets will have SC messages, quitline number and other SC services. If a smoker is willing to accept them and talk to the SCAs, the SCAs will advise the smoker to quit using the AWARD protocol. The AWARD protocol includes (1) Ask the smoking history, (2) Warn about the high risk (i.e., half of the smokers will die of smoking-related diseases), (3) Advise to quit, (4) Refer to the SC clinics of TWGHs and (5) Repeat the above advice (Do-it-again) [4]. Our previous studies have shown that the AWARD protocol is a feasible and appropriate tool used by non-healthcare professionals to promote smoking cessation [4-6]. If the smoker is interested in using the SC services, the SCAs will introduce NRT to the smoker and conduct a preliminary assessment of his/her eligibility for enrolling in the "NRT sampling" programme. The SCAs will invite him/her to go to the smoking cessation

truck nearby to receive counselling by an onsite nurse. If the smoker is not eligible, he/she can still enroll in the cessation service provided by the SC clinics.

11. Intervention: NRT sampling and medication counselling

In the experimental sessions, an onsite nurse will assess whether each participant is fit for using NRT with further assessment on his/her current physical status, medication and blood pressure. If the participant is willing to use NRT to quit smoking and pass the nurse's assessment, he/she will be prescribed the NRT sample, regardless of whether they use NRT for smoking reduction and when the quit day is. The nurse will help the participant decide which type of NRT product (gum: 2mg, patch: 14mg or 21mg) that he/she can use and advise him/her on how to use the NRT based on his/her smoking habit and daily cigarette consumption. In addition, the nurse will deliver medication counselling which addresses five main components: (1) the benefits for using NRT in quitting, (2) withdrawal symptoms due to smoking cessation, (3) side effects of NRT, (4) instructions for using NRT, and (5) making appointments for TWGHs SC clinics. Afterwards, the participant will receive 1-week free NRT and an instruction card about the use of NRT.

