All the smokers who consent to the follow-up will be contacted via telephone or WhatsApp around one week by a nurse or a research assistant after recruitment. The aim of this follow-up is to enquire if there is any progress towards cessation and encourage the use of NRT and/or enrollment in SC services.

At 1-, 3- and 6-month follow-up, the quitting outcomes will be assessed by a trained interviewer through telephone who is blinded to the subject's group status.

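### At the nurse call, a participant who has used the NRT sample and still smokes falls under two opposite instructions (15.1.1.1 and 15.1.1.5), and the instruction to stop makes no exception for the reduction use that Section 11 accepts

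*Combined protocol and SAP*

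**What the plan says.** Section 7 describes NRT as an "effective pharmacotherapy to reduce withdrawal symptoms during early abstinence and smoking reduction", so reduction is part of the stated rationale. Section 11 carries this into prescribing: once the nurse's assessment is passed, "he/she will be prescribed the NRT sample, regardless of whether they use NRT for smoking reduction and when the quit day is".

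Section 15 sets the aim of the contact at about one week, for everyone who consents to follow-up, as being to ask about progress and to "encourage the use of NRT and/or enrollment in SC services".

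Section 15.1.1 then gives the nurse's rules for "Participants who receive NRT samples and whose quit day is within one week after baseline". Two of them matter here:

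- 15.1.1.1, for those who have used NRT: the nurse is to "encourage him/her to obtain additional free NRT by enrolling in the SC clinics for the continuation of NRT use", or to suggest buying it if the person will not enrol. Smoking status is not mentioned.
- 15.1.1.5, for those who smoke while on NRT: "If the smoker has a dual use of cigarettes and NRT, the nurse will advise him/her to stop using NRT to avoid overdose". Reduction is not mentioned.

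Under Section 15.1.2, participants with a later quit day are contacted by a research assistant at about one week. The nurse then calls about one week after the quit day and applies the 15.1.1 rules.

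**The concern.** The sample is given on terms that allow the person to keep smoking while using it. When the nurse calls, the same person can be told to carry on with NRT under one heading and to stop it under another, and the second instruction gives overdose as its reason. A nurse who follows the text faithfully can give either answer.

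Three things are at stake. First, the participant may receive inconsistent safety advice about a study product. Second, the advice bears directly on a secondary outcome, self-reported NRT use at 1 and 3 months. It may also touch the primary outcome of service enrolment, because 15.1.1.1 ties continued NRT to enrolling in a clinic while 15.1.1.5 contains no enrolment message of its own. Third, only experimental-group participants who received a sample meet this fork. The control pathway in Section 15.2 has no counterpart, so any variation between nurses enters one arm only. Nothing in the plan has the nurse record which advice was given.

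**Working it through.** No figure in the plan bears on this point, so the check is a comparison of texts.

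1. **Who receives the sample (Section 11).** Anyone willing to use NRT to quit who passes the nurse's assessment. Reduction use and the date of the quit day are expressly not grounds for withholding it. This is the only operative section that speaks directly to people who will go on smoking.

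2. **Who reaches the nurse rules (15.1.1 and 15.1.2).** Sample recipients with an early quit day reach them about one week after baseline. Those with a later quit day reach them about one week after that day. The research assistant's contact under 15.1.2 lists no advice to stop NRT, so 15.1.1.5 does not govern all use before the quit day.

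3. **Do the two groups overlap?** Let U be participants who have used NRT (15.1.1.1) and D be participants who use NRT and cigarettes together (15.1.1.5). Anyone in D has used NRT, so D lies wholly inside U. The instruction for U is to continue, through a clinic or by purchase. The instruction for D is to stop. Every member of D therefore meets both.

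4. **Is precedence stated?** No. Neither subsection refers to the other, and 15.1.1 gives no order in which to apply them.

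5. **Does treating 15.1.1.5 as an exception remove the conflict?** It settles 15.1.1.1 against 15.1.1.5. It does not settle Section 11 against 15.1.1.5: a participant given the sample on terms that accept reduction use would be told at the call to stop for using it in that way.

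6. **Timing against the outcomes (Section 5, Phase 3).** For an early quit day, the call at about week 1 precedes both 1-month primary outcomes and the NRT-use outcome at 1 and 3 months. For a quit day q weeks after baseline, the call falls at about q + 1 weeks. Taking one month as about four weeks, it precedes the 1-month assessment only if q is below about 3. For later quit days the possible effect is on the 3-month outcomes.

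**The case against.** The strongest reply is that the subheadings under 15.1.1 were never meant to be mutually exclusive. On this reading 15.1.1.1 is the default for users, and 15.1.1.4 (contra-indications) and 15.1.1.5 (concurrent smoking) are narrower safety overrides. Section 15.1.1.4 overlaps 15.1.1.1 in the same way, and few readers would call that a contradiction. This is a reasonable reading, and D lying inside U supports it. But it has to be supplied by the reader, and the conflict with Section 11 survives it.

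A second reply is that Section 11 and 15.1.1.5 act at different times: one governs supply at baseline, the other a call after or around the quit day. This stands as a limit on scope. Much reduction use before a late quit day will never meet 15.1.1.5. It does not help the participant who is still reducing when the nurse calls.

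Third, Section 15's general aim can be met by enrolment alone, and neither it nor 15.1.1.1 mentions people who still smoke. That also stands. They cover such people only by setting no condition, and Section 15's aim is not itself in conflict with 15.1.1.5. Nor does 15.1.1.5 forbid encouraging enrolment, so an effect on that outcome is possible rather than shown.

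Finally, Section 10 of the plan's flow (the paragraph on pragmatic conduct, under Section 11) allows flexible procedures. Its examples concern the order of consent and the mailing of samples, and they do not extend to opposite advice about stopping a study product.

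**Conclusion.** The point holds, within limits. As written, a sample recipient who has used NRT and still smokes at the nurse call is subject to opposite instructions with no stated precedence, and the instruction to stop ignores a use accepted at prescription. This assumes that having used NRT in 15.1.1.1 includes current users, which is its plain meaning. The documents do not say how many participants this affects.

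Two stronger readings are tempting and are not supported.

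- **A head-count.** A reader might combine the pilot's 34% NRT use with the 720 planned sample recipients (0.34 × 720 = 245), subtract the 144 targeted quit attempts, and infer at least 101 affected (101/720 = 14%) and at most 245 (34%). This sets a pilot result at 3 months against a target of this trial. The pilot's own quit-attempt figure of 26% gives 0.26 × 720 = 187, a difference of 58, or 8%, so the supposed floor is not a floor. Neither version is usable: 3-month use is not use at the call, not all 720 reach 15.1.1.5 while still using NRT, and the ceiling treats every NRT user as a concurrent smoker.
- **That the tested intervention is undefined.** This does not follow. The randomised contrast, sample with its instruction card against advice to obtain NRT through the clinics, is set at baseline (or by mail soon after). Randomisation, sample size, outcome definitions and analysis are untouched. What is undefined is one piece of follow-up advice in the experimental group.

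It still needs correcting, because following the text can give one participant contradictory safety-related advice, and the correction is cheap.

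**What to change.** The responsible clinicians should reconcile Sections 11, 15.1.1.1 and 15.1.1.5, together with the routing from 15.1.2, so that a participant who has used NRT and still smokes falls under exactly one stated instruction, consistent with the terms on which the sample was supplied. If one subsection is meant to override another, the text should say so. Which rule is clinically right is for them to decide.

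Add one field to the nurse-call form recording which advice on NRT was given, and report its distribution in the experimental group.

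The document is dated 30 June 2020, the proposed completion date, so the calls may already be complete. In that case, state in the report which advice was actually given, as far as records allow, and say so where it cannot be established.

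The cost is a wording change and one form field, or a short statement in the report. No change to the sample size or analysis is needed.

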In the control sessions, all the above procedures for the experimental group will be applied, except that they will not receive an NRT sample and an instruction card about the use of NRT. Instead, they will be advised to obtain free NRT by enrolling in the SC clinics. Both groups will receive a one-page leaflet provided by the SC clinics.

As this trial is a pragmatic trial, flexible procedures will be adopted based on the actual interaction with the participant. Firstly, the intervention components and filling in of baseline questionnaire may be carried out prior to seeking the consent from the participant if it is deemed more suitable in the situation and can make the procedures run more smoothly. Secondly, if the recruitment venue is not suitable for drug dispensing, the NRT sample and the use instructions will be register-mailed to the participants' address instead of given immediately. All NRT will be prescribed by registered nurses. The research assistant will also contact the participants to confirm that they have received the NRT. This arrangement of mailing the NRT sample complies with the Pharmacy and Poisons Ordinance of the Drug Office.

12. Randomization

We will use cluster randomization based on promotion session as the cluster unit because the procedures of individual randomization are difficult in outdoor areas as found in our pilot RCT. The PI will randomly allocate the promotion sessions within a hotspot to the 2 groups by a list of group allocation which is based on a list of random numbers from Excel programme. Each hotspot will have 2 or more promotion sessions, and each session will last for about 3-4 hours. If a hotspot has 2 promotion sessions on 1 single day, the 2 sessions will be allocated into the same RCT group, and we will organize 2 more promotion sessions in this hotspot on another day.

13. Allocation concealment

All recruitment staff will know the group allocation before each promotion session, so no group concealment can be done.

14. Blinding

Participants cannot and will not be blinded to the intervention. Assessors of the follow-up outcomes and the research analysts will not be involved in the recruitment and intervention delivery, and will be blinded to the group allocation (single blindness).

15. Follow-up

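### For sample recipients with a quit day more than a week away, the nurse's NRT-use, contra-indication and dual-use steps come only after that quit day, although the sample may be used before it

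*Combined protocol and SAP*

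**What the plan says.** **Supply.** Under Section 11, a participant who is willing to use NRT and passes the nurse's assessment gets the sample "regardless of whether they use NRT for smoking reduction and when the quit day is". The quantity is fixed: "the participant will receive 1-week free NRT and an instruction card about the use of NRT".

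**General one-week contact.** Section 15 has a nurse or a research assistant contact every consenting smoker at about one week. The purpose is to ask about progress and to encourage NRT use, SC service enrolment, or both.

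**Quit day within one week (15.1.1).** "A TWGHs nurse who is experienced in delivering smoking cessation will contact the participants around one week after baseline". Smokers are asked whether "they have used any NRT and have any difficulties in using NRT, and will be given more counseling via telephone if necessary". If a smoker reports a contra-indication, "the nurse will advise him/her to stop using NRT to avoid risks" (15.1.1.4). If a smoker is using cigarettes and NRT together, "the nurse will advise him/her to stop using NRT to avoid overdose" (15.1.1.5).

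**Quit day later than one week (15.1.2).** A research assistant makes the one-week contact, sends motivational messages and asks whether the participant needs the TWGHs counsellors. The nurse comes later: "Otherwise, the participants will be contacted by the TWGHs nurse around one week after their quit day as outlined above in section 15.1.1".

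**Other branches.** Sections 15.1.3 to 15.1.5 cover only experimental-group participants who did not receive a sample.

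**The concern.** Supply does not depend on the quit day, but the timing of the nurse's steps does. Recipients with a distant quit day, or who take NRT to cut down, are the ones most likely to smoke while holding the product. That is the situation Section 15.1.1.5 addresses, yet Section 15.1.2 brings its advice to them last.

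The sections also pull in different directions. Section 11 allows supply for smoking reduction, which implies some smoking while on NRT. Section 15 has the one-week contact encourage NRT use. Section 15.1.1.5 has the nurse advise stopping NRT when the two are combined. A late-quit-day recipient who is still smoking at one week could be encouraged to use NRT at that contact and be advised to stop it at the later nurse contact.

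What is at stake is whether the plan's own safety step is applied consistently to everyone given the product, and whether staff following the protocol know which instruction governs.

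**Working it through.** The plan states no figure on this point, so there is none to reproduce. The check is a day count from the plan's own intervals, with baseline as day 0.

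**Inputs**
- Sample length: 7 days (Section 11).
- Nurse contact: about day 7 if the quit day *q* is at most day 7 (15.1.1).
- Nurse contact: about day *q* + 7 if *q* is later than day 7 (15.1.2).
- Start of use *s*: not stated. Day 0 is taken as the early case and the quit day as the late case.

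**Formula.** The sample ends on day *s* + 7. In the 15.1.2 branch, the gap from the end of the sample to the nurse contact is (*q* + 7) − (*s* + 7) = *q* − *s* days.

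| Quit day *q* | Nurse contact | Sample ends if *s* = 0 | Gap if *s* = 0 | Gap if *s* = *q* |
|---|---|---|---|---|
| 7 or earlier | day 7 | day 7 | 0 days | see note |
| 8 | 8 + 7 = day 15 | day 7 | 8 days | 0 days |
| 14 | 14 + 7 = day 21 | day 7 | 14 days | 0 days |
| 21 | 21 + 7 = day 28 | day 7 | 21 days | 0 days |
| 28 | 28 + 7 = day 35 | day 7 | 28 days | 0 days |

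Note: in the first row the contact is fixed at day 7. If use starts on the quit day, the sample ends on day *q* + 7, so the contact comes on or before that end.

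**Reading the table**
1. The earliest whole quit day in the 15.1.2 branch is day 8, so the earliest nurse contact there is about day 15.
2. The gap depends on when use starts. It vanishes if the sample is kept for the quit day and equals *q* days if it is started at once.
3. Nothing in the plan tells recipients to keep the sample for the quit day. Section 11 allows use for reduction, and Section 22 explains on-the-spot supply by the wish that smokers can use NRT once they are motivated.
4. The research assistant's contact at about day 7 does fall before the nurse's in this branch. The content listed for it in 15.1.2 includes no question on NRT use, contra-indications or smoking while on NRT.
5. Sections 15.1.1 and 15.1.2 are both defined by a quit day, and 15.1.3 to 15.1.5 by not having a sample. A recipient with no quit day matches none of these headings.

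**The case against.** The best defence is that late-quit-day recipients are screened before supply and contacted afterwards.

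- **Screening before supply.** Section 9 has medical exclusions. In Section 11 a nurse assesses physical status, medication and blood pressure, then counsels on side effects and use. This stands, and it makes the later contra-indication step a backstop. It does not explain why the backstop comes later for one group.
- **Contact at one week.** Everyone who consents is reached, and 15.1.2 offers counsellor contact. This stands, but the offer depends on the participant saying it is needed.
- **Early-quit-day recipients are hardly better placed.** Their nurse call falls near the end of a 1-week supply, so they too can almost finish the sample first. This stands. The difference between branches is the added delay and the missing NRT question at one week.
- **Use may start on the quit day.** If so, contact a week later is coherent, as the zero gaps in the table show. The point therefore concerns recipients who start earlier, as the plan permits.
- **Reduction users may all have a quit day.** Section 11 supplies people willing to use NRT to quit, and its wording seems to presume a quit day. That a recipient might have none is an inference from the reduction allowance.

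A reader might go further and infer that nobody asks these recipients about NRT again. The documents do not support that: Section 5 schedules self-reported NRT use at 1 and 3 months. Nor do mailed samples go unfollowed, since Section 11 has a research assistant confirm receipt, though receipt is all that contact is said to cover.

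A reader might also infer bias in the 1-month primary outcomes. Taking a month as 30 days, *q* + 7 > 30 when *q* > 23, so a few nurse calls could come after that assessment. This does not bias the comparison: a pragmatic trial estimates the effect of the package as delivered by then.

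**Conclusion.** The point holds as an inconsistency in the plan's follow-up rules. Section 15.1.2 sets a rule, rather than merely omitting a detail, that defers the nurse's NRT steps to about day 15 or later for recipients with a quit day more than one week away. The sample lasts 7 days and may be used before the quit day. With use from day 0, the nurse contact comes at least 8 days after the sample is finished. That figure rests on immediate use and on reading the approximate intervals as exact.

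The number of people affected cannot be computed. Section 16 targets 720 sample recipients, but the documents give no distribution of quit days. A reader might apply an assumed share to the 720; nothing in the plan supports any particular share.

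It would also be too strong to say that reduction users have no pathway, because the general one-week contact covers them if they consent. What is missing is a branch written expressly for a recipient without a quit day.

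**What to change.** The investigators should reconcile Sections 11, 15, 15.1.1 (including 15.1.1.4 and 15.1.1.5) and 15.1.2 on two matters:

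1. Supply regardless of quit day or for reduction, encouragement of NRT use at one week, and the advice on contra-indications and on smoking while using NRT should be consistent with one another.
2. Every sample recipient, including one with a late quit day or none, should fall in one stated pathway for the plan's own NRT steps.

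The clinical team decides the rule, its timing, its content and who carries it out. This review proposes none of these.

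The cost is small: protocol wording, a change to the script of the one-week contact that is already planned, and a few more hand-offs from research assistant to nurse. Sample size and analysis are unaffected.
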